5.2 Device Accountability (if applicable)

Device accountability is not required.

5.3 Device Handling & Storage

All products used in this study are commercially approved.

6.0 PROCEDURES

6.1 Study Flow Chart

Refer to section 1.1 for the study flow chart

CIP

6.2 Procedures

The clinical study will be conducted in accordance with the CIP. All parties participating in the conduct of the clinical study will be qualified by education, training, or experience to perform their tasks and this training will be documented appropriately.

The clinical study will not commence until St. Jude Medical receives written approval from the IRB/EC and relevant regulatory authorities and all required documents have been collected from the Fuwai Hospital.

Table 1: List of all study specific activities/procedures

Table with 3 columns: Visit, Enrollment, Ablation Procedure. Rows include Study Activity, Informed Consent Process, Verification of Inclusion and Exclusion Criteria, Demographics and Medical History, 12-lead ECG, Record Unipolar EGM during mapping, Record Bipolar EGM during mapping, Record successful/unsuccessful ablation sites, Adverse Event, Withdrawal, Deviation, Death.

X: Mandatory CRFs

(X) : CRF will be completed if applicable

The following table lists all Case Report Forms (CRFs) that are to be completed during the respective visits. Mandatory CRFs are identified with an "X". CRFs that are optional or have to be completed only in case of a certain event (i.e. Death) are marked with an "(X)"

Table 2: Case report forms

Table with 3 columns: Visit, Enrollment, Ablation Procedure. Rows include CRFs, Enrollment, Baseline, Ablation Procedure, Adverse Event, Withdrawal.

CIP

CRFs	Visit	Enrollment	Ablation Procedure
Deviation		(X)	(X)
Death		(X)	(X)

X: Mandatory CRFs

(X) : CRF will be completed if applicable

6.3 Enrollment Visit

Patient Informed Consent Process

The following enrollment activities are performed after the subject has been screened and must occur before any study procedure/visit.

- The principal or delegated study personnel are responsible for screening all potential subjects to determine subject eligibility for the study
 - Inform the eligible patient verbally about the investigation and provide the information sheet and consent to the patient.
 - Provide ample time to the patient to read and understand the information sheet and PIC and to consider participation in the clinical investigation.
 - Obtain the signature and date from the eligible patient on the Ethics Committee (EC) approved PIC.
 - If an eligible patient does not sign and date the PIC, he cannot participate in the investigation. No further protocol required activities are performed.
 - Obtain the signature and date from the PI or delegated investigator on the EC approved PIC.
 - The subject is enrolled in the investigation when the patient signed the EC approved PIC.
 - Provide one original signed version of the PIC to the subject (signed by both subject and investigator).
 - File second original signed version of the PIC in the Investigator Site Binder (ISB).
- Record enrollment information (name of the study, date of consent and Inclusion/exclusion information) in the hospital records and complete and submit the Enrollment CRF in a timely manner (recommended within 5 days)
- Notification of enrollment to the sponsor will take place only when the sponsor receives the enrollment form

NOTE: As soon as the subject signs the ICF, adverse events need to be reported according to the guidelines mentioned in section 8.2.

If a subject does not meet all inclusion criteria or meets any of the exclusion criteria, the subject cannot participate in the study and cannot be enrolled.

CIP

In case the subject was already consented to participate in the study, but does not meet inclusion/exclusion criteria, the following actions will be taken.

If study procedure has not occurred:

- Document enrollment information (name of the study, date of consent and inclusion/exclusion) in the hospital records; complete the Enrollment and Withdrawal Forms. The form must be authorized / approved by the principal or delegated investigator.
 - Inform the subject about the withdrawal.
 - The EC/IRB and CA should be notified appropriately about any deviations with regards to obtaining the informed consent.

If study procedure has occurred:

- Document enrollment information (name of the study, date of consent and inclusion/exclusion) in the hospital records; complete the Enrollment and Withdrawal Forms. The form must be authorized / approved by the principal or delegated investigator.
 - Complete study deviation for inclusion/exclusion not met
 - Inform the subject about the withdrawal.
 - The EC/IRB and CA should be notified appropriately about any deviations with regards to obtaining the informed consent.

Demographics and Medical History

- Demographics - include subject's Age and Gender
- Medical History - include subject's height, weight, blood pressure (measurements taken during visit), cardiovascular history (most recent value closest to baseline visit), risk factors, relevant co-morbidities, previous cardiac procedures, VA diagnosis, and medication (only chronic cardiac related medication).

12-lead ECG

Standard 12-lead ECG will be collected. In addition, prior documentation of 12-lead ECG with VAs will be collected if available.

6.4 Ablation Procedure Visit

In case the patient's VA is not present and cannot be induced before the ablation procedure, the ablation should not be performed according to the 2009 EHRA/HRS Expert Consensus on Catheter Ablation of Ventricular Arrhythmias¹. The following actions will be taken:

- Inform the subject about the withdrawal.
- Complete the Withdrawal CRF. The form must be authorized / approved by the principal or delegated investigator

The ablation procedure will be performed according to the Fuwai hospital's standard practice. During the ablation procedure, any clinical adverse events or protocol deviations are to be noted on the appropriate forms. The following information will be collected at the ablation procedure visit:

- Date of procedure

CIP

- The unipolar EGM, the bipolar EGM pairs as defined below, and the 12-lead surface ECG.
- Nonsuccessful and successful ablation sites tagged on the map.
- Acute success rate
- Indicate model and number of mapping and ablation catheters used in the procedure
- Adverse Events, Death, and/or Protocol Deviation notification (if applicable)

Mapping and EGM Recording

A quadripolar ablation catheter will be used to map the target site. Specifically, the unipolar EGM is recorded from the distal electrode (M1) of the mapping catheter and filtered at 0.5~100Hz. The bipolar EGMs are recorded from the distal (M1-M2), mid (M2-M3), and proximal (M3-M4) electrode pairs of the mapping catheter, respectively, and filtered at 30~500Hz. LAT is measured using the distal electrode pair and is defined as the interval between the initial sharp peak of the EGM and the onset of the VA QRS. The presence of the bi-RP is evaluated between the distal and mid electrode pairs and is defined as a rapid simultaneous deflection in the opposite direction of the initial part of the bipolar EGM occurring before the onset of the VA QRS. All the unipolar EGM, bipolar EGMs, and the 12-lead surface ECG will be displayed on the monitor for the physician’s reference and stored on the electrophysiology recording system and on the Ensite Velocity mapping system for off-line analysis. To guarantee accurate electroanatomic activation mapping and to avoid annotation of catheter-induced premature ventricular contractions (PVCs), the VA QRS morphology of each acquired mapping point will be compared to a 12-lead QRS template of the clinical arrhythmia.

Ablation

Radiofrequency energy will be applied at 30W with a maximum temperature of 55 °C for regular ablation catheter, and 35 to 40W with a maximum temperature of 43 °C for irrigated ablation catheter. If the VA is not abolished within 10 seconds of RF ablation, the energy application will be terminated and the ablation site will be tagged as a nonsuccessful site on the map. If the VA is abolished within 10 seconds, the energy application will be continued for a total of 90 seconds and the site will be tagged as a successful site on the map. The procedure endpoint is reached when the targeted VA did not occur spontaneously after a waiting period of 30 minutes and could not be induced by electrical programmed stimulation before and after isoproterenol infusion and Valsalva maneuver.

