2.0 BACKGROUND AND JUSTIFICATION FOR CLINICAL STUDY

Currently, the first-line therapy for symptomatic Ventricular Arrhythmia (VA) patients is still antiarrhythmic drugs¹. Unfortunately, drug therapy is not always effective and can be hindered by side effects¹⁻³. As an alternative, Radiofrequency Catheter Ablation (RFCA) has been shown to be highly effective in treating focal idiopathic VAs in the outflow tract (OT), with acute success rates greater than 80%^{1,4-6}. Although RFCA is generally considered a safe procedure, serious complications may still occur^{1,7-8}. Therefore, it is important to minimize the number of lesions while achieving an effective treatment.

The classic strategy to guide RFCA is based on local activation time (LAT) map and the presence of a QS morphology in the unipolar electrograms (uni-QS)⁹⁻¹². However, the actual LAT at the successful ablation site may vary a lot among patients, and the area demonstrating a unipolar QS morphology may be larger than the focal source⁹⁻¹². In practice, these factors may greatly affect the efficiency of the physicians to locate the focal source and cause unnecessary ablation lesions. Thus, more specific criteria are needed to help guide the search for successful ablation site.

The presence of reverse polarity in adjacent bipolar electrograms (bi-RP) has been demonstrated in pulmonary vein isolation procedure using circular catheter based on the hypothesis that the excitation wavefront propagates radially from the breakthrough site in the pulmonary vein¹⁴. A similar approach using the reversal initial deflection of adjacent bipolar electrograms has been demonstrated in patients with accessory pathways and focal atrial tachycardia¹⁵. Lately, Carine et al., in a retrospective analysis, showed that a method combining the use of LAT and bi-RP phenomenon in focal right ventricular outflow tract (RVOT) arrhythmias could yield a higher specificity for identifying successful ablation sites than the conventional LAT plus unipolar QS morphology method¹⁶.

The proposed study aims to evaluate the predictive value of bi-RP and uni-QS for identifying successful ablation site. It will also evaluate the feasibility to enhance uni-QS method's performance by using uni-QS and its morphology characteristics such as descending slope and symmetry.

CIP

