4.3 Objectives

Primary Objective

Evaluate the predictive value of using reversed polarity in adjacent bipolar EGMs (bi-RP method) and unipolar EGM with QS morphology (uni-QS method) for identifying successful ablation site

Secondary Objective

Evaluate the feasibility of enhancing uni-QS method's performance by using its morphology characteristics such as descending slope and symmetry.

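### Must the plan be changed because it gives no reading rule for uni-QS and no rule for combining it with bi-RP?

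*Combined protocol and SAP*

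**What the plan says.** Section 4.4 sets the primary endpoint as the predictive values of the bi-RP and uni-QS methods, and the secondary endpoint as the predictive value of a new method that puts the two together.

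Section 6.4 (Mapping and EGM Recording) defines bi-RP in operational terms. The distal and mid electrode pairs are compared, and the marker is positive when there is a rapid simultaneous deflection in the "opposite direction of the initial part of the bipolar EGM occurring before the onset of the VA QRS".

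For uni-QS the same paragraph states that "the unipolar EGM is recorded from the distal electrode (M1) of the mapping catheter" and gives a filter of 0.5 to 100 Hz. Section 4.3 identifies the marker as "unipolar EGM with QS morphology (uni-QS method) for identifying successful ablation site". The secondary objective there is to improve uni-QS by "using its morphology characteristics such as descending slope and symmetry".

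LAT is also measured, as the "interval between the initial sharp peak of the EGM and the onset of the VA QRS", but no endpoint uses it. All tracings are "stored on the electrophysiology recording system and on the Ensite Velocity mapping system for off-line analysis". Each acquired mapping point has its QRS compared with a 12-lead template of the clinical arrhythmia.

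Section 11.1 describes the design in one sentence and gives no analysis method. Section 11.2 says the sample size has no statistical basis. Section 11.3 permits, but does not require, an interim analysis once more than 10 subjects are enrolled.

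**The concern.** One of the two primary markers has a written reading rule and the other has little more than a name. A small initial r wave or a notched complex could be called QS by one reader and not by another. The combined method has even less: requiring both markers makes a stricter test, and accepting either makes a looser one.

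The background argues that "more specific criteria are needed to help guide the search for successful ablation site", and cites a retrospective analysis in which LAT with bi-RP "could yield a higher specificity for identifying successful ablation sites than the conventional LAT plus unipolar QS morphology method". The choice of combination therefore bears directly on the study's motivation.

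Sites are tagged as successful or nonsuccessful during the procedure and the electrograms can be analysed off-line. Nothing in the text prevents a rule from being chosen once outcomes are known, possibly after an interim look. The same wording also raises the question whether timing (LAT or a pre-QRS condition) belongs to uni-QS as it does to bi-RP.

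**Working it through.** The plan has no figure to reproduce: it states 20 subjects without a calculation, and gives no error rate, power, sensitivity, specificity or number of sites per patient. The check is a reading of the text, followed by arithmetic on assumed counts.

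**What the text settles**

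- *Beat selection.* The template comparison in section 6.4 limits mapping points to the clinical arrhythmia. Only the choice among several matching beats is open.
- *Timing.* Section 4.3 attaches the uni-QS label to the morphology. Section 2.0 lists the LAT map and uni-QS as separate parts of the classic strategy. In the cited retrospective analysis LAT accompanied both markers, so it is not peculiar to uni-QS. Morphology alone is the natural reading, although the plan does not say so outright.
- *Version of uni-QS in the combination.* Section 4.4 names uni-QS without qualification. Slope and symmetry appear only in the objective.

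Two things remain open: how borderline QS tracings are read, and whether the combination needs both markers or either.

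**Size of the combination gap**

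Among N nonsuccessful sites, let a be positive on both markers, b on bi-RP only and c on uni-QS only.

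- Specificity, both-positive = 1 − a/N
- Specificity, either-positive = 1 − (a + b + c)/N
- Difference = (b + c)/N, the share of sites where the markers disagree

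The same holds for sensitivity at successful sites, with the sign reversed. Neither the sign nor the size of the difference in positive predictive value (PPV) is fixed by logic alone.

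Illustration on assumed inputs. 20 × 0.95 = 19 patients (5% attrition, section 11.2), one successful site each, two nonsuccessful sites each (38). Assumed positives: uni-QS 15/19 and 19/38; bi-RP 15/19 and 8/38. The number positive on both can be 11 to 15 of the successful sites and 0 to 8 of the nonsuccessful ones.

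| Rule | Sensitivity | Specificity | PPV |
|---|---|---|---|
| Both positive | 11/19 to 15/19 = 57.9–78.9% | 30/38 to 38/38 = 78.9–100% | 11/19 to 15/15 = 57.9–100% |
| Either positive | 15/19 to 19/19 = 78.9–100% | 11/38 to 19/38 = 28.9–50.0% | 15/42 to 19/38 = 35.7–50.0% |

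Disagreements at nonsuccessful sites run from 11 to 27, so the specificity gap is 11/38 = 28.9 to 27/38 = 71.1 points. The lower bound is only the difference between the two assumed false-positive counts, (19 − 8)/38. If both markers had 8 false positives, disagreements would run from 0 to 16 and the gap from 0 to 42.1 points. The gap depends on the data; the plan does not fix it.

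**Size of the reading gap**

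With the same counts, uni-QS PPV = 15/(15 + 19) = 44.1%, exact 95% interval 27.2% to 62.1%, ignoring clustering of sites within patients. Re-reading two sites from positive to negative gives at most 15/32 = 46.9% or at least 13/32 = 40.6%, a shift of 2.8 or 3.5 points.

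**Can the gap be filled without a new rule?**

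Yes. A table of bi-RP by uni-QS (positive or negative), split by site outcome, has eight cells. Those cells give each marker alone, both-positive and either-positive. The stored tracings supply every entry.

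**The case for a change.** The strongest case for acting is that a feasibility label explains the absence of a powered sample size but not of an endpoint definition. The plan managed to define bi-RP, and no convention tells an analyst whether combining means both or either. A few sentences would close the matter at almost no cost and would remove any suspicion that the rule was picked after seeing outcomes. The case report forms, supplied separately, might hold a reading field, but the plan does not refer to them for one. A wide change in QS reading could also matter. If a strict reading had sensitivity 0.70 and specificity 0.80, and a loose one 0.95 and 0.40, then with 20 successful and 60 nonsuccessful sites the PPV would be 14/26 = 54% against 19/55 = 35%.

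Most of this stands as a description. The omissions are genuine, and a report giving only the more favourable combination would deserve criticism. But the remedy is to write down a detail, and the objection does not identify a better rule or show that a stated one misleads. Each predictive value is valid once its marker is fixed. No test exists whose error rate could be inflated, and the optional interim look has no stopping or adaptation rule attached. The strict and loose readings are invented extremes for a recognised pattern recorded from a fixed electrode and filter.

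**Conclusion.** The concern is accurate in a narrow form and does not call for a change. The plan leaves open how borderline QS tracings are read and whether the combined method needs both markers or either. The doubts about timing and about which version of uni-QS is combined are largely answered by the natural reading of sections 2.0, 4.3 and 4.4, and beat choice is mostly settled by the template comparison.

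This is a gap that analysts can fill sensibly: apply one QS criterion to every tagged site and show both combinations from the same table. The combination gap equals the rate of disagreement between the markers, which the plan cannot supply and which may be zero or large. The reading gap is small against sampling error if only one or two sites are in doubt.

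The figures rest on 19 evaluable patients with one successful site each, which is optimistic. Section 2.0 reports acute success only as above 80% (0.80 × 19 = about 15), and sections 6.4 and 11.4 also exclude patients whose arrhythmia is absent and cannot be induced. Fewer sites would make every estimate coarser without altering the conclusion.

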4.4 Endpoints

Primary Endpoint

Predictive values of the bi-RP method and uni-QS method for successful ablation

CIP

Secondary Endpoint

Predictive value of a new method by combining bi-RP and uni-QS for successful ablation.

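### Does the pre-QRS condition in the bi-RP rule, with none stated for uni-QS, undermine the two predictive values?

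*Combined protocol and SAP*

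**What the plan says.** Section 6.4 (Mapping and EGM Recording) evaluates bi-RP between the distal and mid electrode pairs and requires a rapid, simultaneous deflection "in the opposite direction of the initial part of the bipolar EGM occurring before the onset of the VA QRS". Timing is therefore part of the rule.

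For the other method, section 4.3 gives only "unipolar EGM with QS morphology (uni-QS method) for identifying successful ablation site". Section 6.4 adds the recording electrode and the filter band, with no timing condition. The same section states how LAT is taken: "LAT is measured using the distal electrode pair and is defined as the interval between the initial sharp peak of the EGM". The other end of that interval is where the arrhythmia's QRS begins. No cut-off and no later use are given.

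The primary endpoint in section 4.4 is "Predictive values of the bi-RP method and uni-QS method for successful ablation". The secondary endpoint combines the two rules, and the secondary objective looks at slope and symmetry of the QS wave. Neither mentions LAT. Section 11.1 is a single sentence naming the design. Sections 11.2 to 11.4 cover sample size, a possible interim analysis and drop-outs.

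**The concern.** Section 2.0 motivates the study with a cited retrospective analysis in which LAT plus bi-RP "could yield a higher specificity for identifying successful ablation sites than the conventional LAT plus unipolar QS morphology method". LAT stood on both sides of that contrast. In the rules written for this study, timing is stated on one side only.

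A reader who places the two predictive values next to each other could therefore credit polarity reversal with a gain that belongs partly to the pre-QRS clause. The clause can raise bi-RP specificity by rejecting late reversals at nonsuccessful sites. It can also lower sensitivity by rejecting late reversals at successful sites. The planned output would not separate these effects, although LAT is measured and the signals are stored for off-line analysis. At stake is how the study's result is interpreted when more specific criteria for finding the ablation site are sought.

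**Working it through.** The plan gives no sensitivity, specificity or effect size, and section 11.2 says that the sample size has no statistical basis. There is no plan figure to reproduce. The check is a comparison of the sections, then an illustration on assumed inputs.

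**1. Is any planned quantity wrong?** The endpoint asks for a predictive value for each rule. A rule with a timing component has a well-defined predictive value, and so does a rule without one. Neither is biased for its own target by the other's definition. No test or contrast of the two is planned.

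**2. Is LAT singled out?** No. Section 11.1 describes no analysis of bi-RP, uni-QS, slope, symmetry or LAT.

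**3. Could timing already enter both sides?** Section 2.0 says "The classic strategy to guide RFCA is based on local activation time (LAT) map and the presence of a QS morphology" in the unipolar signal. Section 6.4 refers to activation mapping and to the hospital's standard practice, and only ablated sites are tagged. If sites are chosen from an activation map, both rules are scored on the same early sites. The plan states no LAT rule for choosing sites, so this is plausible but not certain.

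**4. What could the clause do to bi-RP?** Let s and t be the shares of nonsuccessful and successful tagged sites that show reversal, but not before QRS onset. The clause adds s to specificity and takes t from sensitivity. With success share p and, without the clause, sensitivity Se and false-positive share F:

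PPV with clause = p(Se − t) / [p(Se − t) + (1 − p)(F − s)]

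Assumed inputs, none from the documents: Se = 0.90, F = 0.30, s and t from 0 to 0.10.

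| s | t | PPV at p = 0.20 | PPV at p = 0.50 |
|---|---|---|---|
| 0 | 0 | 0.18/0.42 = 0.43 | 0.45/0.60 = 0.75 |
| 0 | 0.10 | 0.16/0.40 = 0.40 | 0.40/0.55 = 0.73 |
| 0.10 | 0 | 0.18/0.34 = 0.53 | 0.45/0.55 = 0.82 |
| 0.10 | 0.10 | 0.16/0.32 = 0.50 | 0.40/0.50 = 0.80 |

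The shift runs from about −3 to +10 points at p = 0.20 and from about −2 to +7 at p = 0.50. It is zero when s = t = 0. Its sign and size depend entirely on the assumptions.

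**5. Could the study resolve it?** Section 11.2 gives 20 subjects and about 5% attrition: 20 × 0.95 = 19. Section 2.0 puts acute success above 80%: 0.80 × 19 = 15.2. Assume one successful site per successful patient, giving 15 to 19 sites. One site then moves sensitivity by 100/15 = 6.7 to 100/19 = 5.3 points. If no successful site failed the pre-QRS condition, the exact upper 95% limit, 1 − 0.025^(1/n), would still be 21.8% (n = 15) or 17.6% (n = 19).

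For nonsuccessful sites, an assumed 1 to 5 per patient gives 19 to 95 sites and upper limits of 17.6% to 3.8%. These limits treat sites as independent, and clustering within patients would generally widen them.

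The one-site premise is not established by section 6.4. A site is tagged on abolition within 10 seconds, whereas the procedure endpoint is judged after a 30-minute wait and stimulation. A patient could have several tagged successful sites, or one without reaching the procedure endpoint.

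**The case for a change.** The best case for a change is that the background invites comparison and the data are already there. Section 2.0 warns that "the actual LAT at the successful ablation site may vary a lot among patients", and no LAT cut-off governs site choice, so nobody can say in advance that the effect is zero. An analysis section that merely reported predictive values would not reveal the asymmetry. A table of LAT by outcome and by rule status, with bi-RP rescored without its timing clause, would show what the clause contributes, with no new procedure or visit.

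The factual part stands: the definitions differ in timing and LAT has no stated use. It does not amount to a needed correction, for three reasons.

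- Rescoring bi-RP is more than a wording change. It needs another off-line reading of every tagged site, when outcomes are already marked on the map.
- Adding a pre-QRS condition to uni-QS from the distal sharp peak would not equalise the rules, because the bi-RP clause refers to the initial deflection. Degree of earliness would also remain uncontrolled.
- The case report forms are under separate cover and may hold a fuller uni-QS scoring rule. The apparent asymmetry may be silence rather than a choice.

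**Conclusion.** The observation is accurate, but the plan needs no change on this account. Following it as written gives a valid predictive value for each rule, and the point bears only on an informal comparison that the plan does not make. The size is unknown and may be zero. The shifts of a few to about ten points shown above illustrate assumed inputs and are not estimates for this trial.

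Analysts can fill this gap sensibly. A report that states both definitions in full lets readers see that one includes timing, and LAT can be described by outcome from data already held. That is optional description in a feasibility study of about 20 patients. The conclusion rests on the endpoint being read as two separate predictive values. It would need revisiting if a formal claim that one rule outperforms the other were added.
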